We will recruit 280 participants; 70 in each of the four arms. Wiberg-Itzel et al [2] observed mean umbilical artery pH 7.23 (SD 0.07) in the non-intervention group. With our sample size, we will have 80% power (significance level 0.05) to detect mean pH changes of 0.04 and above in each arm. We are interested in detecting an effect size of 0.2 and above, which we deem to be a moderate effect size. The total sample size needed to detect a between-factor mean effect size of 0.2, by repeated measures analysis of variance (ANOVA) with a type 1 error margin of 5%, across 4 groups with 5 repeated measurements; was 224 at a power of 91%. Assuming a 20% loss to follow up in our study; we will need 280 participants (70 in each of the 4 groups). The sample size was calculated using G* Power software version 3.1 using the test family for the F test, and the statistical test for ANOVA repeated measures, between factor analysis & within-between interaction [10]. Therefore, our sample size will also be sufficient to detect a within and between-subject interaction (intervention and time interaction) with a power of 99%. To obtain these estimates, we will construct an interaction term between the intervention and the time variable. We are confident that we shall be able to accrue this number of participants in a period of six calendar months, on the basis of our experience working in the same hospital [7]. In order to detect a change in maternal pH, a minimum of two measurements are needed from a participant. However, with improvement of obstetric care, many women deliver within 30 minutes of taking the baseline measurements and hence no second measurement is obtained. To account for this form of right censoring, we have inflated our sample size by 192 participants to ensure that we have at least 280 women with at least two pH measurements. We will recruit 472 participants; 118 in each of the four arms.

Outcome variables

The primary outcome measure will be the mean change in maternal pH from baseline in each group. The secondary outcomes will include, mean pH and lactate in maternal and umbilical blood, early neonatal death, safety (side effects) of sodium bicarbonate, primary PPH, sepsis and death. Furthermore, the plasma concentrations of HCO₃ levels will be measured as well to accurately estimate the required dose.

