Secondary outcomes will include neonatal death, postpartum haemorrhage and sepsis, in addition to the pharmacokinetics of sodium bicarbonate infusion in pregnant women. Details of measurements are in table 1.

The independent variables will include the sociodemographic, clinical, and obstetric characteristics of the study participants at different time points as indicated in table 1.

Table 1: Measurements to be taken from the participant samples

Activity/ procedure	Time in minutes							Comment
	Baseline (0)	30	60	90	120	150	At birth	
Metabolites (lactate & glucose)	X	X	X	X	X	X		Bedside using the RAPID Point 500e or YSTE-BG100 Blood gas analyzer
Blood gases (pH, pCO ₂ , pO ₂)	X	X	X	X	X	X	X	
Serum Electrolytes (Na ⁺ , K ⁺ , Ca ²⁺ , Cl ⁻)	X	X	X	X	X	X	X	
Umbilical cord blood for lactate							X	Bedside using the RAPID Point 500e or YSTE-BG100 Blood gas analyzer
Myometrial Lactate only collected at Caesarean section							X	Bedside using the RAPID Point 500e or YSTE-BG100 Blood gas analyzer
Creatinine	X							Total of 5 mL of venous blood will be taken to a central laboratory; these are part of the standard care for each patient.
Liver function tests (ALT&AST)	X							
Full blood count	X							
Amniotic fluid lactate*	X							Lactate Pro device
Bicarbonate concentrations in plasma	X	X	X	X	X	X	X	Bedside using the RAPID Point 500e or YSTE-BG100 Blood gas analyzer

[figure not shown]

Figure 2: Flow of participants in the trial from screening to analysis

Recruitment and data collection from participants

Participants: Obstructed labour will be diagnosed by either an obstetrician or medical officer using a definition of the American Association of Obstetricians and Gynaecologists (ACOG). In the first stage of labour, the participant should have cervical dilatation >6 cm with ruptured membranes, adequate contractions lasting >4 hours with no change in cervical dilatation or delay in the second active stage of labour (nullipara >2 hours, multipara >1 hour) with adequate uterine contractions. In addition, any two of: the obvious signs of severe obstruction such as caput formation, severe moulding, Bandl's ring, subconjunctival haemorrhages or an oedematous vulva.

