Our research assistants will be qualified midwives with training in data collection, using dedicated password protected android devices. We will also review relevant health facility records such as antenatal care cards, case notes/file, the maternity and theatre registers. Laboratory parameters including lactate will be measured at baseline, and every thirty minutes after study drug administration until delivery to obtain samples for lactate measurement in umbilical cord blood and the myometrium. The participants will be followed for 7 days postnatal to ascertain the secondary perinatal outcomes and for 14 days postpartum to determine the secondary maternal outcomes. In the first 24 hours after study drug administration, the participants will be closely monitored to identify any drug reactions/adverse events. After administration of the study drug, all the participants will be actively monitored by a research midwife up to 24 hours. The women will be examined and asked directly about the presence of side effects.

Sample collection quality control

Qualified and well-trained research midwives will draw five millilitres (ml) of blood by venipuncture at the antecubital fossa of the non- dominant arm from each participant using a five millilitres syringe. After removing the epidermal needle and the tops of the vacutainers, two millilitres will be emptied into a purple top vacutainer for a full blood count, blood grouping and cross-matching as part of the standard preoperative preparation for all patients with obstructed labour in the hospital. The remaining three millilitres will be emptied into a red top vacutainer for blood chemistries including electrolytes, these are not part of the routine preoperative preparation for patients before caesarean section. Each blood sample will be transported to the laboratory in an ice-cooled container within 30 minutes of collection. Urine samples: Mid-stream urine, ten millimeters will be collected in sterile urine container from the mothers. We will monitor strict adherence to the standard operating procedures for collecting and handling participant samples through ongoing training and spot checks.

Cord blood collection

After the baby is born, the midwife will double clamp and cut the umbilical cord. Cleanse a 4" - 6" area of the umbilical cord with alcohol to remove maternal blood and contaminants (before the delivery of the placenta, if possible). Then blood will be drawn from the cord with a needle.

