Data analysis plan

Data will be analyzed using Stata version 17.0 (StataCorp; College Station, TX, USA). We will describe categorical variables as proportions and compare them with chi-squared tests or Fischer's exact tests as appropriate. We will describe continuous variables as means (SD) OR medians (IQR) and compare them with t tests or Mann-Whitney U tests as appropriate. Our analysis will be by intention to treat. To determine the safety of sodium bicarbonate infusion, we will compare the incidence of side effects in each arm and report risk differences.

For the primary outcome of acidosis (pH and lactate) between-subjects repeated measures ANOVA will be conducted. We will also conduct within-subject interaction repeated measures ANOVA to assess for differences in the rate of change of pH between the groups.

We will use histograms, P-P plots, k-density, and Q-Q to assess the distribution of normality of continuous outcomes. In case the distribution of normality is not met; we shall transform our data and this decision will be guided by Stata's *gladder* command that shows various transformation options.

All analyses will be followed by a Bonferroni posthoc test for multiple comparisons, a Friedman test to compare rates of change between the various groups, and a Mauchly's test of Sphericity to check for equal variance among the combinations of the various groups. We will use Margins and Margins plots to obtain marginal means and graphical descriptions of the interaction between various groups and time.

Data Monitoring

Independent Data Monitoring Committee (IDMC)

An independent data monitoring committee (IDMC) will be appointed consisting of 3 members: a statistician, an obstetrician/gynaecologist, and a paediatrician. They will operate according to the IDMC charter, which will be developed with the members. IDMC will be encouraged to follow the recommendations of the international DAMOCLES group for IDMC activities.[12] The IDMC will monitor the trial once with a focus on issues relating to the quality of trial conduct, such as overall and site-specific rates of recruitment, adherence to trial interventions, visit schedules, losses to follow-up, and administrative and safety data. It will review administrative and safety data approximately every three months. The treatment groups will be masked in the IDMC reports.

Interim analyses and stopping guidelines

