Dissemination and Publications															*	*	*	*

Pharmacokinetics of sodium bicarbonate

Study design: This will be a population-based pharmacokinetics study of sodium bicarbonate using plasma levels in pregnant women with obstructed labour. We propose to investigate the association between the exposure of various doses of sodium bicarbonate (i.e. 8.4g, 12.6g and 16.8g) in pregnant women with obstructed labour, and identify determinants to inform dosing policy guidelines.

Study population: We will establish a cohort of pregnant women with obstructed labour in Mbale regional referral hospital. Only mothers that consent to participate in the study will be included.

Data collection: Following the administration of sodium bicarbonate, a blood sample will be collected from the mother at time 30, 60, 90, 120 and 150 minutes and at the time of childbirth; and then umbilical cord blood will be collected at birth for testing. Consequently, the concentrations of sodium bicarbonate will be determined using liquid chromatography (HPLC) method with electrochemical detection as described by Rodriguez [19]. The HPLC analysis will be conducted at Busitema University Ministry of Science, Technology and Innovation supported laboratory. Data from the respective participants will include PK, socio-demographics, adverse events and other clinical parameters including weight and age.

Data analysis: Non-compartmental analysis will be used to analyse the intensive PK data for sodium bicarbonate and a population pharmacokinetic model will be developed to analyse the sparse PK data. Any disparate treatment approached, additional medications or relevant clinical information, will be captured and adjusted for in the model. We will use nonlinear mixed-effects modelling (also known as population PK) to interpret the sodium bicarbonate pharmacokinetic data and assess the effect of variation. PopPK modelling offers a semi-mechanistic platform to interpret PK data, in that it evaluates the effect of patient covariates on physiological PK parameters (such as clearance and bioavailability), as opposed to hydroxyurea concentrations summary values (such as AUC and C_{max}). The concentration-time data for the drugs of interest will be analysed using popPK (nonlinear mixed-effects) modelling in NONMEM.

References

1. Wray S: **Insights into the uterus**. *Experimental Physiology* 2007, **92**(4):621-631.

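### Cord pH and lactate have no four-arm model or dose-versus-placebo estimate, and the pre-dose maternal values go unused; the cost is precision and interpretability

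*Combined protocol and SAP*

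**What the plan says.** All references are to the combined protocol and SAP.

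- **Outcome variables** lists the cord measures as secondary: "The secondary outcomes will include, mean pH and lactate in maternal and umbilical blood".
- **Table 1** schedules the cord sample once, at birth. Its cord row reads "Umbilical cord blood for lactate" and does not name pH. The newborn section of the data collection tool (Appendix 1) does have cord rows under blood gas and pH columns, so cord pH appears to be intended.
- **Data analysis plan** gives repeated measures ANOVA to the primary outcome: "For the primary outcome of acidosis (pH and lactate) between-subjects repeated measures ANOVA will be conducted". For continuous variables in general it says to describe them and "compare them with t tests or Mann-Whitney U tests as appropriate". It also provides for a transformation, guided by a Stata command, when normality fails.
- The same section adds: "All analyses will be followed by a Bonferroni posthoc test for multiple comparisons". It does not say how many comparisons make up the family.
- Risk differences are promised for side effects, and marginal means for the group-by-time analysis. No between-arm estimate is promised for cord outcomes.
- **Data collection** provides the possible covariates: "Laboratory parameters including lactate will be measured at baseline, and every thirty minutes after study drug administration until delivery". Table 1 marks maternal lactate and blood gases, including pH, at time 0. No analysis names a baseline covariate.

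**The concern.** A t test or a Mann-Whitney test compares two groups, and this trial has four. Without named contrasts, the analyst must decide later whether to run three dose-placebo comparisons or all six pairs. The analyst must also choose between a t test, a rank test and a transformation once the data are in. These answer different questions: a mean difference, a rank comparison, or a difference on another scale.

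The trial is meant to find a dose and to inform a full-scale trial, and its rationale is resuscitation of the fetus in the womb. What the next trial needs from the cord data is an estimate for each dose against placebo, with its uncertainty. The plan does not promise one. It also sets aside pre-dose maternal measurements that may predict the cord values and would then sharpen those estimates at no cost.

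**Working it through.** **Plan's own figures.** With f = 0.2, four groups, five measurements, alpha 0.05 and N = 224, and an assumed within-woman correlation of 0.5, the noncentrality is 224 × 0.2² × 5 / (1 + 4 × 0.5) = 14.93 on 3 and 220 df. Power is 91.1% (stated 91%), and 224/0.8 = 280. Both reproduce, but they concern the serial maternal values. The only cord figures in the Sample size section are a pH SD of 0.07 and a difference of 0.04, which is 0.04/0.07 = 0.57 SD. No cord lactate SD is given, so lactate can be treated only in SD units.

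**Familywise error per cord outcome** (400,000 simulated null trials with four equal arms):

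| Contrasts | No correction | Bonferroni |
|---|---|---|
| 3, dose vs placebo | 12.5% | 4.4% |
| 6, all pairs | 20.2% | 4.1% |

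The Bonferroni sentence therefore controls the error within each outcome, whichever family is chosen. Across cord pH and lactate together, the bound for three contrasts each is 2 × 4.4% = 8.8%.

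**What the undefined family costs in power.** Cord pH difference 0.04, SD 0.07, two-sided, normal approximation:

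| Per arm | alpha 0.05 | 0.05/3 | 0.05/6 |
|---|---|---|---|
| 70 | 92% | 84% | 77% |
| 118 | 99% | 98% | 96% |

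A cord sample does not require a second maternal measurement, so the number available may be nearer 118 than 70.

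**What the unused baseline costs.** If the pre-dose maternal value correlates r with the cord value, adjustment multiplies the residual variance by 1 − r². The standardised difference d becomes d/√(1 − r²), and the noncentrality is that value × √(118/2). Take d = 0.3 (an assumption) and 118 per arm. The four-arm model has 467 residual df (468 unadjusted), and its critical t is 1.965 at 0.05 and 2.403 at 0.05/3.

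| r (assumed) | 1 − r² | Effective d | Noncentrality | Power, 0.05 | Power, 0.05/3 |
|---|---|---|---|---|---|
| none | 1 | 0.300 | 2.304 | 63.3% | 46% |
| 0.1 | 0.99 | 0.302 | 2.316 | 63.7% | 47% |
| 0.3 | 0.91 | 0.314 | 2.416 | 67.4% | 51% |
| 0.5 | 0.75 | 0.346 | 2.661 | 75.7% | 60% |
| 0.6 | 0.64 | 0.375 | 2.880 | 82.0% | 68% |

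Ignoring the covariate is like discarding a share r² of the sample: 9% at r = 0.3 and 25% at r = 0.5.

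At the plan's own 0.57 SD there is less to gain. With 70 per arm and alpha 0.05/3, power goes from 84% to 84%, 88%, 93% or 97% at r = 0.1, 0.3, 0.5 or 0.6. With 118 per arm it is already 98%.

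**The case against.** The strongest reply has four parts.

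1. **No sentence says that cord outcomes get a t or Mann-Whitney test.** True. The words come from a general sentence on continuous variables. That leaves either this rule or no rule, and both leave the four-arm comparison unspecified.

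2. **The plan already handles multiplicity.** This stands. A reader might infer a false-positive risk of 12.5% to 20% per cord outcome, but those figures require ignoring the sentence that puts a Bonferroni step after all analyses. What remains open is the size of the family.

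3. **Leaving out a covariate is not an error.** This also stands. Under randomisation it costs precision and causes no bias. The maternal sample is taken before dosing and comes from a different circulation. The protocol puts the average wait for caesarean at about 110 minutes, so a low correlation, with almost no gain, is plausible.

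4. **Skewed lactate is already covered by the transformation provision.** In part. A log scale is available under the plan, but so is a rank test, and nothing says which takes precedence.

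A reader might also take cord chemistry to be the only fetal evidence in the trial. The documents do not support that. Early neonatal death is a secondary outcome, Apgar scores and day-7 newborn status are collected, and the pharmacokinetic part states that "then umbilical cord blood will be collected at birth for testing".

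**Conclusion.** The point holds as a specification gap in secondary outcomes. For cord pH and lactate the plan names no four-arm model, no contrasts, no effect estimate with an interval and no baseline covariate, although suitable pre-dose values are collected. Type I error within each outcome is controlled if the Bonferroni sentence is applied, and no bias arises.

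The size of the precision loss is uncertain. For 0.3 SD at 118 per arm and alpha 0.05, adjustment adds under half a point of power at r = 0.1 and about 19 points at r = 0.6. This rests on three assumptions: the 0.3 SD difference, the correlation, and a cord sample from all 118 women per arm. At the 0.57 SD implied by the plan's pH figures and 118 per arm, power is high with or without adjustment. In that case the main benefit is a clear estimate for each dose. The primary analysis is unaffected.

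**What to change.** For cord pH and cord lactate, replace the t/Mann-Whitney choice with this wording in the Data analysis plan:

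- Fit one linear model per outcome, with arm (four levels) and the pre-dose maternal value of the same analyte as covariate. Fix the log scale for lactate in advance.
- Report the three dose-minus-placebo adjusted differences (ratios for lactate) with 95% confidence intervals.
- Apply the plan's Bonferroni step to those three contrasts within each outcome, testing at 0.05/3 = 0.0167. State that the 95% intervals are not adjusted for multiplicity.

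Add pH to the cord row of Table 1, so that it agrees with the Outcome variables section.

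The cost is wording only. The covariate is scheduled at time 0, so it should also exist for women who deliver before a second maternal sample. No new data, participants or procedures are needed.

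### The primary outcome is change in maternal pH from baseline, but the first-named primary test compares mean level without baseline adjustment, and the plan names neither the deciding test nor a rule for women who deliver early

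*Combined protocol and SAP*

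**What the plan says.** All references are to the Combined protocol and SAP.

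- **Outcome variables:** "The primary outcome measure will be the mean change in maternal pH from baseline in each group".
- **Data analysis plan:** for the primary outcome, described here as acidosis measured by both pH and lactate, a "between-subjects repeated measures ANOVA will be conducted". The next sentence adds a "within-subject interaction repeated measures ANOVA to assess for differences in the rate of change of pH between the groups". Neither sentence mentions a change score, a baseline covariate or the handling of missing times. The section also states "Our analysis will be by intention to treat", and lists Mauchly's test, Bonferroni comparisons and "a Friedman test to compare rates of change between the various groups".
- **Sample size estimation and sampling:** 224 women give 91% power for a between-factor effect of 0.2 with four groups and five measurements. Allowing for 20% loss makes this 280. Because "many women deliver within 30 minutes of taking the baseline measurements and hence no second measurement is obtained", 192 more are added, for a total of 472, so that 280 have at least two pH values.
- **Timing:** Table 1 schedules blood gases at 0, 30, 60, 90, 120 and 150 minutes and at birth. The Data collection section has half-hourly sampling end at delivery. The Intervention/Comparator paragraph puts the average wait for caesarean at about 110 minutes.
- **Birth sample:** the pharmacokinetics section says "a blood sample will be collected from the mother at time 30, 60, 90, 120 and 150 minutes and at the time of childbirth". Appendix 1, section F, has maternal pH rows for 0 to 150 minutes only. The birth table in section H has a maternal pH column, but its only rows are arterial and venous cord blood.

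**The concern.** The between-subjects effect in a repeated measures ANOVA is a comparison of each woman's average level over the times entered. Randomisation makes the arms equal at baseline in expectation. If baseline is one of those times, it therefore pulls the arm difference towards zero; if it is left out, its information is lost. Neither version estimates change from baseline.

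Two ANOVA tests on two variables (pH and lactate) are attached to the primary outcome, and none is named as decisive. The interim stopping rule, which refers to a significant difference in the primary outcome, inherits that gap.

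Delivery also truncates the pH series. Setting aside women who deliver before a second sample selects on an event after randomisation. Recruiting more women restores the numbers but does not remove the selection.

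Finally, the Friedman test ranks repeated values within women. It carries no between-arm comparison, so it cannot compare rates of change between arms.

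**Working it through.** **Inputs.** From the sample size section: effect size f = 0.2, alpha 0.05, four groups, N = 224 for five measurements, and 280 women with at least two pH values. Assumed: a common correlation ρ between times, which the plan does not give. I use 0.5, with 0.3 and 0.7 as a range. The arm effect is taken as constant after baseline and zero at baseline.

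**Reproducing the plan's figure.** Noncentrality λ = f²·N·m/(1+(m−1)ρ) = 0.04 × 224 × 5/3 = 14.93. With 3 and 220 degrees of freedom, power is 91.1%, against the stated 91%. So ρ = 0.5 is consistent with the plan's calculation. Also 224/0.8 = 280, 280 + 192 = 472, and 192/472 = 40.7%.

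**Power for 280 women with baseline plus k later values.** λ = 280 × 0.04 × R, where
- baseline averaged in: R = (k/(k+1))² / ((1+kρ)/(k+1));
- baseline as covariate: R = 1 / ((1+(k−1)ρ)/k − ρ²).

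For k = 1 and ρ = 0.5, R = 0.25/0.75 = 0.333 and λ = 3.73 with baseline averaged in. With the covariate, R = 1/0.75 = 1.333 and λ = 14.93. For k = 5, R = 0.694/0.583 = 1.190 (λ = 13.33) and R = 1/0.35 = 2.857 (λ = 32.0).

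| Later pH values | Baseline averaged in | Baseline as covariate |
|---|---|---|
| 1 | 33% | 91% |
| 2 | 61% | 98% |
| 3 | 76% | over 99% |
| 4 | 83% | over 99% |
| 5 | 87% | over 99% |

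For one later value, the pair is 38% and 84% at ρ = 0.3, and 30% and 98% at ρ = 0.7.

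**The arm-by-time test with one later value.** With two times this is the change-score test, with R = 1/(2−2ρ). At ρ = 0.5, λ = 280 × 0.04 = 11.2 and power is 81%.

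**Reaching the late times.** The documents give only a mean wait of about 110 minutes. If waits were exponential, 472 × exp(−120/110) = 159 women (34%) would be undelivered at 120 minutes and 472 × exp(−150/110) = 121 (26%) at 150 minutes. Exponential, gamma and lognormal shapes with that mean give 22% to 37% at 120 minutes and 11% to 26% at 150 minutes.

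**pH at birth.** Table 1 marks blood gases at birth without saying maternal or cord. Its only explicit cord row is for lactate, yet umbilical pH is a secondary outcome, so either reading is possible. The maternal birth sample in the pharmacokinetics section is for bicarbonate by HPLC. The sample size section says that early deliveries yield no second measurement, and Appendix 1 has no clear row for maternal pH at birth. These places do not agree.

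**The case against.** The strongest reply is that change is tested. The arm-by-time ANOVA is in the plan, the sample size section describes the interaction term and gives it 99% power, and with two values per woman it is the change-score test. This stands. A reader might infer that the trial never tests its primary outcome, and the documents do not support that. What remains is that the interaction is introduced as an additional analysis and no deciding test is named.

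A second reply is that 280 women with two values each still have 91% power: λ = 0.04 × 280 × 2/1.5 = 14.93. That requires f = 0.2 at both times, but one of the two guaranteed values is baseline, where no arm difference is expected.

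Third, a reader might infer that the ANOVA needs every time point and so has far less power than stated. With 121 complete sets, for example, it would be 64%. No section requires complete sets; the stated requirement is two pH values, and a long-format ANOVA keeps partial series. Smaller counts, obtained by letting 40.7% deliver in every half hour, imply a mean wait of 30/−ln(0.593) = 57 minutes, against the stated 110. Such figures describe one possible handling, not the plan.

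Fourth, a reader might infer that a maternal pH at birth is assured for every woman. As shown above, the documents conflict on this.

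**Conclusion.** The concern holds in this form: the first-named primary test does not match the primary outcome, the deciding contrast is not named, and missing times have no stated handling. Where baseline is averaged in, power is 33% to 87% for one to five later values, against 91% to over 99% with baseline as covariate. The 33% applies only if every woman has exactly one later pH. The sizes rest on ρ = 0.5, a constant post-baseline effect and f = 0.2; at 0.3 and 0.7 the covariate analysis remains well ahead for one later value.

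Many women will lack the 120 and 150 minute values. The documents do not show that most miss the times from 30 to 90 minutes. If only complete sets were analysed, most women would be dropped, but the plan does not say so. Expecting about 192 of 472 women to have no second pH is hard to square with intention to treat. The risk is selection on early delivery; its direction and size cannot be derived from the documents. The Friedman test is misassigned whatever is assumed.

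**What to change.** - Make the primary analysis a linear mixed model of all available post-baseline maternal pH values, with baseline pH, arm, time and arm-by-time. Name each dose against placebo as the primary contrasts, and state the time, or average over times, at which they are read.
- Use an unstructured covariance only for the fixed 30 to 150 minute times, simplified if the late times are sparse. It is not defined for a birth sample taken at a different time in each woman. If the birth value is included, use actual time with a continuous-time or random-effects covariance.
- Reconcile Table 1, the sample size section, the pharmacokinetics section and Appendix 1 on whether maternal pH is measured at birth. If it is, add the form field and count it as a post-baseline value, so that early deliveries stay in the analysis. If it is not, say how women with no post-baseline pH are reported under intention to treat.
- Delete the Friedman test, and Mauchly's test along with the ANOVA. Judge differences in rate of change by the arm-by-time term.

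The cost is a small rewording of the analysis section, possibly one form field, and a birth value taken at a varying time that the model must accommodate. The change should be made before the interim analysis.
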